## **6.5 Software Version**

All analyses will be performed using SAS® software Version 9.4 or higher.

# **7 STATISTICAL CONSIDERATIONS**

---

## **7.1 Sample Size Determination**

Approximately 30 adults with CIndU, having either cold urticaria or symptomatic dermographism, will be enrolled in this study.

## **7.2 Multicenter Studies**

This study will be conducted by multiple investigators at multiple sites in the USA. Data from all sites will be pooled together in the summaries and analyses.

## **7.3 Handling of Dropouts or Missing data**

Unless otherwise specified in the sections below, no missing data will be imputed.

### **7.3.1 Efficacy Data**

#### **7.3.1.1 Observed Cases**

No missing data will be imputed, and the analysis will be based on observed data only.

### **7.3.2 Safety Data**

Partially or completely missing medication and AE start and stop dates will be imputed as described in [Appendix 2](#) and will only be used for the classification of each medication as prior or concomitant (refer to Section 11) and each AE as prior or treatment-emergent (refer to Section 14.1). That is, imputed dates will not be used to compute duration and will not be presented in subject data listings.

## **7.4 Descriptive Statistics**

Unless otherwise indicated, continuous endpoints will be summarized using descriptive statistics i.e., number of subjects with non-missing data (n), mean, standard deviation (SD), median, minimum, and maximum.

[REDACTED]

Categorical endpoints will be summarized using frequencies and percentages.

### **7.5 Adjustment for Covariates and/or Fixed Effect**

Not applicable.

### **7.6 Coverage of Confidence Intervals and Statistical Tests**

Confidence intervals (CIs) will be two-sided with 95% coverage.

No statistical tests will be performed.

### **7.7 Multiple Comparisons/Multiplicity**

No adjustments for multiple comparisons/multiplicity will be made for this study.

### **7.8 Examination of Subgroups**

[REDACTED]

## **8 STUDY SUBJECTS**

---

[figure not shown]
### **8.1 Disposition of Subjects**

All subjects who provide informed consent will be accounted for in this study. The number of subjects screened and rescreened will be presented. The number and percentage of subjects with screen failure will be presented for all screened subjects, except for those who were rescreened and did not fail the second screening. Reason for screen failure will be summarized similarly but for subjects with screen failure.

The number of subjects enrolled (i.e., who provide informed consent and are eligible to continue in the study) will be presented for each treatment group and overall. Number and percentage of subjects included in each population, who completed or discontinued early from study drug, and who completed or discontinued early from study will be presented for all enrolled subjects. Reason for discontinuation from study drug and/or reason for discontinuation from study will be presented similarly but for subjects who discontinued early from study drug and/or who discontinued early from study, respectively.

Number of days in the study will be calculated as follows and summarized overall:

(Date of completion/discontinuation – Date of first dose of study drug) +1

A listing of subject's disposition will be provided. Information on first screening for subjects who were rescreened, including the rescreened subject identifier, will be presented under the first screening subject identifier. A listing of subject's enrollment information and a listing of subjects included/excluded from each of the populations, with reason for exclusion, will also be provided.

## **8.2 Protocol Deviations**

Protocol deviations are classified as Major or Minor. Classification will be based on the Protocol Deviation Management Plan (PDMP). The PDMP refers to Important/Non-Important classification and these will be considered as Major/Minor PDs for the purpose of the analysis, respectively.

The number of events and the number and percentage of subjects with at least one major protocol deviation will be summarized by treatment group and overall, deviation category and sub-category based on the safety population. Site-level protocol deviations will be reported once for each subject enrolled at that site.

A listing of all protocol deviations will be provided and major will be flagged.

## **9 DEMOGRAPHIC AND OTHER BASELINE CHARACTERISTICS**

---

Demographic and other baseline characteristics will be summarized using descriptive statistics by treatment group and overall based on the safety population. The list of demographic and baseline characteristics to be summarized includes:

- Age (years) as collected on electronic Case Report Form (eCRF)
- Sex at birth
- Ethnicity
- Race
- Baseline height (cm)
- Baseline weight (kg)
- Baseline body mass index (BMI) ( $\text{kg}/\text{m}^2$ ), derived as the baseline weight (kg) divided by the square of the baseline height ( $\text{m}^2$ ) i.e., baseline height (m) x baseline height (m)
- Disease history of symptomatic dermatographism or cold urticaria

- Time since diagnosis of symptomatic dermographism or cold urticaria

- [REDACTED]

Subjects who reported more than one race will be counted once under each reported race.

The time since diagnosis of symptomatic dermographism or cold urticaria will be calculated as:

Time since diagnosis = (Date of first dose of study treatment – Date of diagnosis)/365.25.

Completely or partially missing dates for the date of diagnosis will be imputed as follows:

- Completely missing: Leave missing.
- Missing day and month: Impute to January 1st.
- Missing day: Impute to the 1st of the month.

A listing of all demographics and other baseline characteristics will be provided.

## 10 SURGICAL AND MEDICAL HISTORY

---

Surgical and medical history will be coded according to the Medical Dictionary for Regulatory Activities (MedDRA), version 27.0.

Incidence of surgical and medical history will be summarized by system organ class (SOC) and preferred term (PT), by treatment group and overall based on the safety population. Subjects who experienced the same surgical and medical history multiple times within the same SOC will be counted only once for the corresponding SOC. Similarly, subjects who experienced the same surgical and medical history multiple times within the same PT will be counted only once for the corresponding PT. Surgical and medical history will be sorted alphabetically by SOC and within each SOC, PTs will be presented by decreasing order of overall frequency.

A listing of all surgical and medical history will be provided.

## 11 PRIOR AND CONCOMITANT MEDICATIONS

---

Medications will be coded according to the World Health Organization Drug Dictionary (WHO-DD), version B3 Mar 2024.

Prior medications are defined as any medication started and discontinued prior to the first dose of study drug. Concomitant medications are defined as any medication taken on or after the first dose

[REDACTED]

of study drug including those who started prior to the date of the first dose of study drug and continued past that date. [REDACTED]

[REDACTED]

Incidence of prior medications will be summarized by anatomical therapeutic chemical (ATC) class level 3 and preferred drug name, by treatment group and overall based on the safety population. Subjects with multiple medications within the same ATC class level 3 will be counted only once for that ATC class level 3. Similarly, subjects with multiple medications within the same preferred drug name will be counted only once for that preferred drug name. Prior medications will be sorted alphabetically by ATC class level 3 and within each ATC class level 3, the preferred drug name will be presented by decreasing order of overall frequency.

Concomitant medications will be summarized similarly.

Medications received for urticaria will be split into prior and concomitant medications similarly and summarized separately.

A listing of all medications (prior and concomitant) and a listing of all medications received for urticaria will be provided.

Furthermore, the use of antihistamines by the subjects, and whether the medication qualifies as a short-acting or long-acting antihistamine, will be reviewed, flagged, and confirmed by the Medical Monitor prior to database lock. This information will be used for the purpose of the sensitivity analysis as defined in section 13.4.

## **12 EXPOSURE TO AND COMPLIANCE WITH STUDY DRUG**

---

Duration of exposure to study drug, in days, is defined as follows:

$$(\text{Date of last dose of study drug} - \text{Date of first dose of study drug}) + 1$$

Compliance with study drug (%) will be calculated as follows:

$$\frac{\text{Total number of doses taken}}{\text{Number of Expected Doses}} \times 100$$

[REDACTED]

The number of doses taken corresponds to the number of expected doses per day x duration of exposure (days), minus the number of doses missed between the first dose and last dose of study drug per eCRF reporting.

[REDACTED]

- [REDACTED]  
[REDACTED]  
[REDACTED]  
[REDACTED]  
[REDACTED]
- [REDACTED]  
[REDACTED]  
[REDACTED]  
[REDACTED]

Duration of exposure to study drug (days), and compliance with study drug (%) will be summarized using descriptive statistics based on the safety population.

Study drug administration, accountability, exposure, and compliance will be listed.

## 13 EFFICACY ANALYSES

---

Unless otherwise specified, all efficacy endpoints will be summarized by visit, when applicable, and by treatment group based the efficacy population.

### 13.1 Definition of Efficacy Endpoints

#### 13.1.1 TempTest

The TempTest is an instrument used to elicit symptoms of cold and heat urticaria. A positive response to the provocation test is defined as a palpable wheal at the test site. Approximately 10 minutes after completion of provocation (i.e., approximately 15 minutes from the start of the test), the resultant wheal will be outlined on the TempTest provided stencil. The critical threshold temperature (CTT), defined as the highest temperature that elicits a wheal response, will be determined and recorded.

[REDACTED]

[REDACTED]

[REDACTED]

The proportion of subjects who are complete responders [REDACTED] will be calculated at Weeks 1, 2, and 4.

The proportion of subjects categorized as at least partial responders will also be calculated at Weeks 1, 2 and 4. [REDACTED]

### 13.1.2 FricTest

The FricTest is an instrument used to diagnose symptomatic dermographism. The FricTest is a flat plastic comb (85 x 55 mm) with four round-ended plastic pins 3 mm in diameter, numbered 1 – 4, with length of 3.0, 3.5, 4.0, and 4.5 mm, respectively. For provocation, the comb is held perpendicular to the volar forearm and constant sufficient pressure is applied so that all pins make contact with the skin and are almost, but not completely, invisible. The instrument is then stroked across the skin across approximately 60 mm. After about 10 minutes, the resultant wheals are evaluated. A clearly visible and palpable linear wheal with a width of  $\geq 3$  mm (the diameter of the pins) is considered a positive response. The total number of linear wheals with a width of  $\geq 3$  mm is the Total Fric Score (TFS).

[REDACTED]

Additionally, the proportion of complete responders [REDACTED] will be calculated at Weeks 1, 2, and 4.

The proportion of subjects categorized as at least partial responders will also be calculated at Week 1, 2 and 4. [REDACTED]

### 13.1.3 Pruritus-NRS

Prior to and approximately 10 minutes after completion of the provocation test (right after the wheal evaluation), the subject will be asked to rate the severity of their pruritus at the site of the provocation test [REDACTED]

Overall change in pruritus after provocation will be calculated at Weeks 1, 2, and 4 and compared to baseline, such that:

[REDACTED]

[REDACTED]

[REDACTED]

Additionally, change from baseline after provocation will be calculated at Weeks 1, 2, and 4 and compared to the mean post-provocation scores at baseline, such that:

[REDACTED]

[REDACTED]

The proportion of at least partial responders, and complete responders will also be calculated at Weeks 1, 2 and 4. [REDACTED]

[REDACTED]

[REDACTED]

## 13.2 Main Analysis

For all analyses on the TempTest, only subjects with cold urticaria will be considered. For all analyses on the FricTest, only subjects with symptomatic dermographism will be considered.

Mean change from baseline in efficacy parameters will be summarized using descriptive statistics at each post-baseline visit. The 95% CI will be provided for the mean change and will be calculated using the t-distribution. Analysis will be performed on the observed cases (OC) only and no imputation will be made for missing data.

Proportions of subjects achieving efficacy parameter criteria will be summarized by frequency counts and percentages with 95% CIs at each post-baseline visit. The Clopper-Pearson method will be used for the calculation of the CIs. Analysis will be performed on the observed cases (OC) only and no imputation will be made for missing data. For proportion endpoints, percentages will be based on the number of subjects with a response at the specified visit.

Similarly, a combined analysis on the FricTest and TempTest (for both partial and complete responders) will be performed. In the at least partial responder analysis, a subject will be considered a partial responder if they meet the criteria for partial responder of either the TempTest or the FricTest. In the complete responder analysis, a subject will be considered a complete responder if they meet the criteria for complete responder of either the TempTest or the FricTest.

Subgroups analyses are defined in [section 7.8](#).

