12.2. Early Withdrawal of Study Subjects

The Investigator will make every reasonable effort to keep each subject in the study; however, a subject may voluntarily withdraw from study participation at any time. If the subject withdraws consent and discontinues from the study, the Investigator will attempt to schedule an Early Termination/Study Exit visit as soon as possible, determine the reason for discontinuation, and record the reason in the subject's study records and in the eCRF.

If at any time during the study, the Investigator determines that it is not in the best interest of the subject to continue, the subject will be discontinued from participation. The Investigator may discontinue a subject at any time if medically necessary. The Investigator may discontinue a subject's participation if the subject has failed to follow study procedures or to keep follow-up appointments. Prior to discontinuing a subject from study participation, the Investigator will discuss his/her intentions with the Sponsor Physician or designee. Appropriate documentation in the subject's study record and eCRF regarding the reason for discontinuation must be completed.

All subjects who fail to return to the study center for the required follow-up visits will be contacted by phone to determine the cause(s) why the subject failed to return for the necessary visit or elected to discontinue from the study. If a subject is unreachable by telephone after a minimum of two documented attempts (one attempt on two different days), a registered letter will be sent requesting that subject contact the site regarding study follow-up.

Subjects will be discontinued early from the study if any of the following occur:

- Withdrawal of informed consent (subject's decision to withdraw for any reason).
- Any clinical AE, laboratory abnormality, or inter-current illness which, in the opinion of the Investigator, indicates that continued treatment and/or participation in the study is not in the best interest of the subject.
- Death.
- Serious protocol violation, including persistent non-compliance, subjects requiring prohibited medications or procedures allowing subjects to receive the appropriate medical

attention. In such cases, the Investigator must contact the Sponsor or designee, as the final decision to withdraw the subject will be taken by the Sponsor.

- Discontinuation of the study by the Sponsor.

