12.3. Study Drug Discontinuation

Subjects who discontinue or have their study drug discontinued prematurely should continue to have all protocol-specified safety assessments and end of study procedures collected.

The Investigator should stop study drug treatment in the following instances:

- [REDACTED]
- Inter-current illness that would, in the judgment of the Investigator, affect assessments of clinical status to a significant degree.
- Any AE which is clinically significant, is deemed persistent, is probably or definitely related to study drug in the judgment of the Investigator.
- Unacceptable toxicity.

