#### Output Conventions

TLF will be generated using SAS® and will be displayed on letter size paper with landscape orientation, 1 inch margin, and 9 pt Courier New font.

The header section will comprise the sponsor's name, protocol number, delivery description, data cut-off date or date of database lock, as applicable, and page number (Page X of Y).

TLF title section will include TLF number, TLF title, and population.

[figure not shown]
The footer section will include the source listing(s) (if applicable), list of abbreviations, TLF footnotes, name of the SAS program name, and date and time of the execution of the program.

For categorical summary tables, percentages will be reported to one decimal place. Percentages between 0 and 0.1 (both exclusive) will be displayed as "<0.1" and percentages between 99.9 and 100.0 (both exclusive) will be displayed as ">99.9". Percentages will be based on total number of subjects in the population, except for efficacy and laboratory data where the percentages will be based on the number of subjects with available data.

For descriptive statistics, the minimum and maximum values will keep the same number of decimal places as the original value; the mean and median will be displayed with one additional decimal place than the original value; and the SD, standard error (SE), and CI will be displayed with two additional decimal places than the original value. If derived endpoints are to be summarized, the number of decimals of the derived values is to be chosen on a case-by-case basis, but the rule above applies.

P-values between 0.001 and 0.999, both inclusive, will be reported to 3 decimal places, p-values less than 0.001 will be reported as "<0.001", and p-values greater than 0.999 will be reported as ">0.999".

Listings will be ordered by treatment group, subject number, endpoint/test, date of assessment/collection/measurement, and time of assessment/collection/measurement, if applicable. Imputed dates and imputed missing data will not be presented in the listings. For visit names, nominal visit names will be presented followed by the analysis visit name when both are different (e.g., 'Unscheduled/Week X', etc.) Otherwise, only the nominal visit names will be presented.

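### Responder percentages drop subjects with no result at the visit; a fixed-denominator analysis counting missing as non-response should be shown, preferably as the main one

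*SAP*

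**What the plan says.** SAP 13.2 (Main Analysis) sets the denominator: "For proportion endpoints, percentages will be based on the number of subjects with a response at the specified visit". SAP 7.3.1.1 gives the missing-data rule for efficacy: "No missing data will be imputed, and the analysis will be based on observed data only". Appendix 1 of the SAP (Output Conventions) uses the whole population as the denominator "except for efficacy and laboratory data where the percentages will be based on the number of subjects with available data". Taken together, these make observed cases the deliberate choice for complete responders and at-least-partial responders on the TempTest, the FricTest and the pruritus scale, and for the combined analysis.

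For the intervals, SAP 13.2 says "The Clopper-Pearson method will be used for the calculation of the CIs" and SAP 7.6 says "Confidence intervals (CIs) will be two-sided with 95% coverage". SAP 7.6 also says "No statistical tests will be performed".

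Other provisions bear on who may have no result:

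- Protocol 12.2 lists reasons for early discontinuation. They include adverse events and "Serious protocol violation, including persistent non-compliance, subjects requiring prohibited medications"; for the latter group the sponsor takes the final decision.
- Protocol 12.3 says subjects who stop study drug early "should continue to have all protocol-specified safety assessments and end of study procedures collected". It does not mention the remaining provocation tests.
- SAP 3.3 does not replace subjects who discontinue.
- SAP 6.4 uses a retest, unscheduled or early-termination result for a visit when the scheduled one is absent and the result falls in the window.
- SAP 13.3 repeats the main analysis in the per-protocol population, but names only the change endpoints.
- SAP 11 has antihistamine use flagged for a sensitivity analysis in 13.4. The text of 13.4 is redacted.

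**The concern.** A responder percentage from observed cases describes the subjects who were still being tested. Readers will usually take it as the proportion of treated subjects who responded. The two agree only if those without a result would have responded at the same rate as those with one.

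Several listed reasons for leaving (adverse events, persistent non-compliance, need for prohibited medication) could go with a poorer outcome. The study is open label with no untreated or placebo group, and no tests are planned. The percentage and its interval are therefore the whole responder result, and no control group shares any distortion. Results are shown by dose group, and the TempTest and FricTest analyses are further limited to one subtype, so a few missing subjects can move a percentage visibly.

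Prohibited medication raises a related problem. A subject who takes it, stays in the study and is tested counts as observed. The visible main analysis has no rule for such a result, so it could count as a response.

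**Working it through.** The plan has no figure to reproduce. The sample size of about 30 rests on clinical considerations, and no response rate, dropout rate or power is stated.

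**Inputs from the documents:** about 30 subjects (Protocol 6.2, SAP 7.1); two dose groups of unstated size (SAP 3.3); observed-case denominator (SAP 13.2); two-sided 95% Clopper-Pearson intervals (SAP 7.6 and 13.2).

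**Assumptions:** N dosed subjects (30 overall, or 15 per dose group if split evenly), x responders, and m subjects with no in-window result.

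**Step 1. Observed cases against missing as non-response.** The observed-case rate is x/(N-m) and the fixed-denominator rate is x/N. Their ratio is N/(N-m), whatever x is.

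For N = 30 and x = 12, the fixed-denominator rate is 12/30 = 40.0% (95% CI 22.7 to 59.4) for every m:

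| m | Observed cases (95% CI) | Factor | Excess, points |
|---|---|---|---|
| 1 | 12/29 = 41.4% (23.5 to 61.1) | 30/29 = 1.03 | 1.4 |
| 3 | 12/27 = 44.4% (25.5 to 64.7) | 30/27 = 1.11 | 4.4 |
| 6 | 12/24 = 50.0% (29.1 to 70.9) | 30/24 = 1.25 | 10.0 |
| 9 | 12/21 = 57.1% (34.0 to 78.2) | 30/21 = 1.43 | 17.1 |

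The excess in points grows with the response rate. With 3 of 30 missing it is 2.2 points at 6 responders (22.2% against 20.0%) and 6.7 at 18 responders (66.7% against 60.0%).

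For N = 15 and x = 6, the fixed-denominator rate is 6/15 = 40.0% (16.3 to 67.7). Observed cases give 6/14 = 42.9% with 1 missing, 6/13 = 46.2% with 2, and 6/12 = 50.0% (21.1 to 78.9) with 3.

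**Step 2. Observed cases against the true rate.** Let d = m/N. The true rate is (1-d) × p_obs + d × p_miss, so the bias of the observed-case rate is d × (p_obs - p_miss). With d = 0.20 and p_obs = 0.40:

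- p_miss = 0: 0.20 × 0.40 = +8 points
- p_miss = 0.20: 0.20 × 0.20 = +4 points
- p_miss = 0.40: 0
- p_miss = 0.60: 0.20 × (-0.20) = -4 points

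The sign depends on the missing subjects. With 3 of 30 missing and 12 responders, the rate over all 30 lies between 12/30 = 40.0% and 15/30 = 50.0%. The observed-case 44.4% is inside that range.

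**Step 3. Prohibited medication without withdrawal.** Suppose 2 of 12 counted responders among 30 had taken prohibited medication and stayed in. The report would give 12/30 = 40.0%; with those two counted as non-responders it is 10/30 = 33.3%. Counting missing results as non-response does not change this, because these results are not missing.

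**The case against.** The best defence is that the choice is open, stated consistently, and modest in effect. Treatment lasts four weeks, so few results may be missing. With 1 of 30 missing and 12 responders, the excess is 1.4 points beside an interval about 37 points wide (59.4 - 22.7 = 36.7). Safety is the primary objective and efficacy is descriptive. SAP 13.2 gives counts and SAP 8.1 gives population sizes and discontinuation reasons, so a reader can largely rebuild an all-subject rate. Counting missing as non-response can itself err low when a visit is missed for unrelated reasons. All of this stands and limits the severity. It does not remove the value of a prespecified fixed-denominator result with its own interval.

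Some stronger readings that a reader might infer are not supported:

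- **That the rate is inflated as a matter of fact.** This is certain only relative to missing as non-response, given at least one responder and one missing subject.
- **That treatment failures drop out of the calculation.** Lack of efficacy is not a visible reason for withdrawal. A subject whose wheals persist and who attends is counted as a non-responder.
- **That needing prohibited medication removes a subject.** Only withdrawal, on the sponsor's decision, or a missed test does so.
- **That only safety assessments continue after study drug is stopped.** Protocol 12.3 names what should continue and does not exclude provocation tests. The schedule of assessments is redacted, and in-window early-termination results are used.
- **That the denominator is literally the responders.** Appendix 1 settles that available data is meant.
- **That no safeguard exists.** SAP 13.4 is redacted and may hold a partial one.

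**Conclusion.** The point holds in a limited form. Responder percentages exclude subjects with no in-window result, and the visible text has no responder analysis that counts them as non-responders. The rate is overstated if the missing subjects respond less often than those observed, which is plausible but not shown.

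The size relative to missing as non-response is a factor of N/(N-m). Across the assumed 1 to 6 missing of 30, this is 1.03 to 1.25, or 1.4 to 10.0 points at 12 responders. The missing counts, the responder counts and the even split into dose groups are all assumptions.

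Severity is moderate. The endpoints are secondary and descriptive and nothing is tested, so type I error and power are not affected. What is affected is how the reported rate reads in a study without a control group.

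**What to change.** 1. For every responder endpoint, add a fixed-denominator analysis: all dosed subjects of the relevant subtype (all dosed subjects for pruritus and the combined analysis), with a missing result counted as non-response. Preferably make this the main responder analysis and keep the observed-case table beside it.
2. Report the number of subjects with no result at Weeks 1, 2 and 4, with reasons, by dose group and subtype.
3. State in the same analysis how results obtained after prohibited medication are counted, unless the redacted 13.4 already does so.
4. Reword the denominator sentence in SAP 13.2 to refer to subjects with a non-missing assessment at the visit, in line with Appendix 1.

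The cost is about one SAP paragraph and one denominator change in programming, with no new data collection. Where results are missing, rates will be less favourable, slightly so if few are missing, and may be conservative if visits are missed for unrelated reasons. Showing both tables lets the reader judge that.
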